8.2. Study Entry Criteria

8.2.1 Inclusion Criteria

A subject will be eligible for study participation if he or she meets all of the following criteria:

1. Subject is ≥ 18 years old.
2. Subject has known diagnosis of LI.
3. Subject has moderate to severe (IGA 3–4) LI on the IGA of LI severity.
4. Subject has signed an ICF at Screening before any investigational procedures.
5. Subject who is participating in optional photography has signed a photography ICF.
6. Subject who is participating in the optional PK substudy has signed a PK ICF.
7. Subject is not of childbearing potential, i.e., a female who is postmenopausal (absence of menstrual bleeding for 1 year before Baseline, without any other medical reason, hysterectomy or bilateral oophorectomy),

OR

- Subject is a woman of childbearing potential (WOCBP) or a male subject with sexual partners capable of reproduction who agrees to use 2 effective forms of contraception during the study and for at least 1 month after the last study drug application. The 2 authorized forms of contraception are condom used with 1 of the following methods of contraception:
 - bilateral tubal ligation
 - combined oral contraceptives (estrogens and progesterone) or implanted or injectable contraceptives with a stable dose for at least 1 month before Baseline; hormonal contraceptives must inhibit ovulation
 - hormonal intrauterine device (IUD) inserted at least 1 month before Baseline

OR

Agrees to abstain from heterosexual intercourse during study participation and for 1 month after the last application of study drug and to use a highly effective contraceptive as backup if he or she becomes sexually active during the study. Abstinence is only acceptable if this is the subject's usual lifestyle. Periodic abstinence (calendar, symptothermal, postovulation methods), withdrawal (coitus interruptus), spermicides only, and lactational amenorrhoea method are not acceptable methods of contraception.

AND

Male subjects may not donate sperm during the study and for at least 1 month after the last study drug application.

8. Women of childbearing potential must be nonlactating and have negative pregnancy test results at Screening (serum) and on Day 1 before study drug administration (urine).
9. Subject is reliable and capable of adhering to the protocol and visit schedule, in the investigator's judgment, and has signed informed consent.
10. Subject is taking no more than 3500 IU/day Vitamin A (e.g., as in a multivitamin).

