10.1. Study Duration

10.1.1 Overall Study Schedule

The overall study duration is expected to be approximately 19 months.

The planned sequence and maximum duration of the study periods will be as follows:

1. Screening: up to 35 days (after signing informed consent, if necessary, washout may be up to 3 months, and subjects should return to the site after washout to complete the study eligibility requirements).
2. Double-blind treatment: Twice weekly for 12 weeks.
3. Optional Open-label Extension treatment: Twice weekly for 12 weeks.
4. Follow-up: 14 days after last study drug application.

The maximum treatment duration for each subject is approximately 12 weeks for subjects who choose not to continue into the OLE, and 24 weeks for those who choose to continue.

The maximum study duration for each subject is approximately 229 days (33 weeks).

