10.2.3 Follow-up Telephone Call (± 14 days after Day 90) – Only Subjects Who Do Not Continue into Open-label Extension

Clinic staff will telephone subjects who choose not to continue into the Open-label Extension within 14 days after Day 90 to assess any ongoing AEs.

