10.2.4.7 Follow-up Evaluation – Open-Label Extension (Week 26/Visit 11)

At 14 days after the last administration of the IP, the following procedures will be performed:

1. Perform a physical examination.
2. Record vital signs (blood pressure and pulse).
3. Record any concomitant medications/therapies.
4. Record IGA.
5. Record VIIS.
6. Assess roughness.
7. Record palm/sole assessment.
8. Record palm/sole assessment of fissuring.
9. Record ectropion score.
10. Assess and record AEs occurring since the last evaluation and review diary.
11. Perform a urine pregnancy test for WOCBP.

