11.2. Event Assessment and Follow-up of Adverse Events

The occurrence of an AE or SAE may come to the attention of study personnel during study visits and interviews of a study participant presenting for medical care or upon review by a study monitor.

All reported AEs, including local and systemic AEs not meeting the criteria for SAEs, will be captured on the appropriate eCRF. Information to be collected includes event description, time of onset, clinician's assessment of severity, relationship to study product (assessed only by those with the training and authority to make a diagnosis), and time of resolution/stabilization of the event. All reported AEs occurring while on study must be documented appropriately regardless of relationship. All reported AEs will be followed to adequate resolution.

Any medical condition that is present at the time that the participant is screened will be considered as baseline and not reported as an AE. However, if the study participant's condition deteriorates at any time during the study, it will be recorded as an AE.

Changes in the severity of a reported AE will be documented to allow an assessment of the duration of the event at each level of severity to be performed. AEs characterized as intermittent require documentation of onset and duration of each episode.

Study clinic personnel will record all reportable events with start dates occurring any time after informed consent is obtained until 14 (for nonserious AEs) or 30 days (for SAEs) after the last day of study participation. At each study visit, the investigator will inquire about the occurrence of AE/SAEs since the last visit. Events will be followed for outcome information until resolution or stabilization.

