11.3.2 Pregnancy

All WOCBP who participate in the study should be counseled on the need to practice highly effective birth control and on the importance of avoiding pregnancy during study participation. Women should be instructed to contact the investigator or study staff immediately if pregnancy occurs or is suspected.

Pregnancy testing will be conducted prior to administration of the IP on every woman of childbearing potential. A woman who is found to be pregnant at the Screening Visit will be excluded from the study and considered to be a screening failure.

A woman who becomes pregnant during IP treatment will be immediately discontinued from study treatment. The investigator must report the pregnancy of any woman who becomes pregnant during or within 30 days after discontinuing treatment as if it were an SAE within 24 hours of learning of the pregnancy, to Premier Research Pharmacovigilance using the Pregnancy Data Collection Form via the same fax number and/or email address as for SAE reporting. The

investigator should contact the designated individual(s) who receive SAE notification and record information related to the pregnancy on an SAE and AE form (entering the event temporarily as nonserious on both forms) provided by the sponsor or its designee. If a partner of a male study subject becomes pregnant, the investigator must report the pregnancy as soon as possible after learning of it to the Premier Research Pharmacovigilance using the Pregnancy Data Collection Form. A separate pregnant partner ICF will be required.

Early Termination Visit assessments are required as soon as possible after learning of the pregnancy in a study subject. The investigator is also responsible for following the pregnancy until delivery or termination. These findings must be reported on the Exposure in Utero form and forwarded to the designated individual(s). The event meets the SAE criterion only if it results in a spontaneous abortion or a congenital anomaly.

Among the clinical studies, 12 pregnancies were reported: 4 resulted in normal births; 5 resulted in spontaneous abortions (none of which was considered related to CD5789); 1 was electively aborted, and 2 were lost to follow-up (IB for CD5789 Cutaneous Formulation).

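### For subjects who do not enter the open-label extension, the follow-up call may be made on Day 91 and asks only about ongoing AEs, so about 12 of the 14 TEAE-window days can pass with no active inquiry

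*Protocol*

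**What the plan says.** Section references are to the Amendment 2 text of the protocol. Part of a later version is also in the file, but without its section 10, so it cannot be checked whether the wording of the call was changed there.

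**Follow-up call, subjects not entering the OLE.**
- Section 10.2.3, text: a call "within 14 days after Day 90 to assess any ongoing AEs".
- Section 10.2.3, heading: plus or minus 14 days around Day 90.
- Table 2-1, footnote c: within 14 days after Day 90, with no earliest day.
- Section 10.1.1, repeated in the synopsis: "Follow-up: 14 days after last study drug application".

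**Follow-up visit, OLE subjects.** Section 10.2.4.7: "At 14 days after the last administration of the IP, the following procedures will be performed". The list includes AEs since the last evaluation and a urine pregnancy test.

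**Periods the follow-up has to serve.**
- Section 11.1.6: treatment-emergent AEs run to 14 days after the last application.
- Section 13.1.6.2: they run to the Follow-up Visit or the Early Termination Visit, whichever comes first.
- Section 11.2: events are recorded "until 14 (for nonserious AEs) or 30 days (for SAEs) after the last day of study participation".
- Section 11.3.2: the investigator must report the pregnancy of "any woman who becomes pregnant during or within 30 days after discontinuing treatment".
- Section 8.2.1, criterion 7: contraception is required "during the study and for at least 1 month after the last study drug application".

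**The concern.** The call is the only scheduled contact after Visit 6 for a subject who does not continue, and its timing is stated in three ways that do not agree. The loosest of them lets a site close follow-up the day after Visit 6.

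The content is narrow too. The Day 97 call covers safety in general and Visit 11 asks for AEs since the last evaluation; only this call is limited to ongoing events. Section 11.2 has a general rule to ask about new AEs and SAEs at each study visit, but does not say whether the call counts as one. These subjects also leave Visit 6 without a new diary, since diaries are dispensed there only for the OLE.

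At stake is the completeness of the TEAE count. Collection would depend on which day a site happened to call, and would differ between subjects who continue and those who do not. If the call counts as the Follow-up Visit of section 13.1.6.2, an early call also shortens the analysis window itself. Section 5.3 says the safety margin for teratogenicity may be lower at higher concentrations or larger areas, so the 30-day pregnancy period matters as well.

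**Working it through.** **The plan's own figure.** The stated maximum study duration is about 229 days (33 weeks). Screening 35 + treatment to Day 180 + follow-up 14 = 229 days, and 229 / 7 = 32.7 weeks. The figure reproduces. It contains 14 days of follow-up and no 30-day contact.

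**Permitted call days, non-OLE.** Heading: 90 − 14 = Day 76 to 90 + 14 = Day 104. Text and footnote c: Day 91 to Day 104.

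**TEAE window against the call.** Visits with PK sampling must be at least 24 hours after an application, so with Visit 6 on Day 90 the latest last application is Day 89. Window end = last application + 14. Days without inquiry = window end − call day.

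| Last application | Window ends | Left after a Day 91 call | Left after a Day 104 call |
|---|---|---|---|
| Day 89 (latest possible) | Day 103 | 12 of 14 | 0 |
| Day 86 (assumed: 4-day gap in a twice-weekly pattern) | Day 100 | 9 of 14 | 0 |
| Day 84 (assumed: dosing stops at exactly 12 × 7 days) | Day 98 | 7 of 14 | 0 |

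Both calls comply, so coverage ranges from complete to about 2 of 14 days (14 − 12 = 2). Because the call asks only about ongoing AEs, even a Day 104 call need not pick up an event that began after Visit 6.

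**Early terminators.** The Visit 6 column of Table 2-1 also serves as the early termination visit, and footnote c hangs on that column, but its words count from Day 90. The call is for subjects who choose not to continue, and someone who stops early may never face that choice. Whether they get the call, and counted from when, is not settled.

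**30-day SAE period (section 11.2, from the last day of participation).** If the call is that day, the period runs to Day 91 + 30 = Day 121, or Day 104 + 30 = Day 134. For OLE subjects it runs 30 days past Visit 11. In each case all 30 days follow the last scheduled contact.

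**30-day pregnancy period (section 11.3.2, from the end of treatment).** Non-OLE: last application Day 89, last test Day 90, period ends Day 119, so 119 − 90 = 29 days follow the last test. OLE completers: 30 − 14 = 16 days follow the last test and contact.

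**The case against.** The strongest reply is that a recording period extending beyond the last contact is not a contradiction. Section 11.2 counts from the last day of participation, so any schedule leaves that whole period after the final contact. Passive routes exist: section 11.2.6.2 requires suspected serious reactions to be reported with no time limit, and section 11.3.2 has women contact the site at once if pregnancy occurs or is suspected. The protocol nowhere promises a contact or test at 30 days. All of this stands, and it limits what can be said about the 30-day periods. It does not rescue the call, whose own timing is inconsistent and whose question is too narrow for the 14-day window.

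A reader might infer more than the text supports:
- *That late events are missed.* They are not actively sought and may be missed; the passive routes remain.
- *That nobody is covered to 30 days after treatment.* Subjects who stop the drug but stay in the study keep their visits (section 8.4; Table 2-1, footnote b). Someone stopping on Day 20 is still tested at Days 30, 60 and 90, which is 10, 40 and 70 days later; a Visit 5 held 7 days early, on Day 53, is 33 days later.
- *That an early terminator who stops on Day 20 waits 70 to 84 days for the call* (90 − 20 to 104 − 20). That takes Day 90 literally. It is at least as natural to count from the early termination visit.
- *That a reported 30-day event rate would be biased.* No such rate is planned; the TEAE definitions stop at 14 days or at the follow-up or early termination visit.

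**Conclusion.** The point holds for subjects who do not enter the OLE. Their follow-up call is defined inconsistently, may fall on Day 91, and asks only about ongoing AEs. At worst about 12 of the 14 TEAE-window days have no active inquiry. This assumes Visit 6 on Day 90 and a last application on Day 89; with an earlier last application the same call leaves 7 to 9 days. How many sites would call that early is unknown, so the number of events lost cannot be estimated. For early terminators the timing is unclear rather than demonstrably wrong.

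OLE subjects are not affected by the fault in the call. For completers in both groups, no scheduled contact reaches the end of the 30-day SAE or pregnancy period. That is a mismatch between reporting duties and schedule for the sponsor to reconcile, and does not show that a required procedure was left out. The conclusion rests on the Amendment 2 wording.

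**What to change.** 1. In section 10.2.3 (heading and text) and Table 2-1 footnote c, count the call from the last application, as section 10.1.1 already does, with an earliest day no sooner than the end of the 14-day TEAE window. For a Day 89 application that is Day 103, inside the range allowed now.
2. State that the call also applies to early terminators.
3. Have it record new as well as ongoing AEs and SAEs.
4. Reconcile the TEAE end-points in sections 11.1.6 and 13.1.6.2, and say whether the call counts as the Follow-up Visit.
5. Reconcile the anchors in sections 11.2 (last participation) and 11.3.2 (end of treatment), and both 30-day periods with the 14-day schedule. Whether to add a 30-day contact or a pregnancy test is the sponsor's decision.

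The cost is small: items 1 to 3 add no visit; some calls come later than now (by 12 days if the alternative was Day 91) and take slightly longer.

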10.2.4 Open-label Extension

Subjects who successfully complete (i.e., have reliable visit attendance and compliance with IP application, in the investigator's opinion) the initial 12 weeks of double-blind treatment may choose to continue into an optional 12-week OLE with trifarotene cream HE1 200 $\mu\text{g/g}$. During the OLE, subjects will return to the site at Weeks 14, 16, 20, 24, and 26. Additional PK samples will be drawn at Week 16 and 24 from all subjects who continue into the OLE.

10.2.4.1 Telephone Visit (Day 97)

Clinic staff will telephone subject to assess safety (AEs) and to record concomitant medications/therapies. Staff will instruct subject on study drug application, advise subjects regarding permitted emollient(s) for use on nontreatment days (use of emollient(s) on study drug treatment days within 4 hours of study drug application is prohibited), and remind subjects not to apply IP on visit days until after the visit. An unscheduled clinic visit may be performed, if necessary.

10.2.4.2 Visit 7 (Week 14; Day 104 ± 5 days)

The following procedures will be performed at this study clinic visit:

1. Record concomitant medications and concomitant therapies.
2. Record vital signs (blood pressure and pulse).
3. Record IGA.
4. Record VIIS.
5. Record assessment of roughness.
6. Record palm/sole assessment.
7. Record palm/sole assessment of fissuring.
8. Record ectropion score.
9. Assess and record local tolerance/AEs and review diary.
10. Collect returned study drug tubes; confirm study drug compliance by weighing returned tube contents and reviewing diaries.

11. Weigh new study drug tubes and dispense enough additional study drug until next visit, and new diary.
12. Instruct subject on study drug application, and advise subjects regarding permitted emollient(s) for use on nontreatment days; use of emollient(s) and/or sunscreen on study drug treatment days within 4 hours before or after study drug application is prohibited. Remind subjects that 24 hours must have elapsed since IP application before the subject's next visit. Subjects should not apply IP on visit days until after the visit. at the Week 16 and Week 24 Visits, and not to apply IP on visit days until after the visit.

10.2.4.3 Visit 8 (Week 16; Day 120 ±7 days)

The following procedures will be performed at this study clinic visit:

1. Record concomitant medications and concomitant therapies.
2. Record vital signs (blood pressure and pulse).
3. Record IGA.
4. Record VIIS.
5. Record assessment of roughness.
6. Record palm/sole assessment.
7. Record palm/sole assessment of fissuring.
8. Record ectropion score.
9. Assess and record local tolerance/AEs and review diary.
10. Perform a 12-lead ECG.
11. Perform a urine pregnancy test for WOCBP.
12. Collect blood and urine for routine laboratory tests (subject must be fasting at least 8 hours).
13. Collect a PK blood sample (all subjects)
14. Collect returned study drug tubes; confirm study drug compliance by weighing returned tube contents and reviewing diaries.
15. Weigh new study drug tubes and dispense enough additional study drug until next visit, and new diary.
16. Instruct subject on study drug application, and advise subjects regarding permitted emollient(s) for use on nontreatment days; use of emollient(s) and/or sunscreen on study drug treatment days within 4 hours before or after study drug application is prohibited. Remind subjects not to apply IP on visit days until after the visit.

10.2.4.4 Telephone Visit (Day 134)

Clinic staff will telephone subject to assess safety (AEs) and to record concomitant medications/therapies. Staff will instruct subject on study drug application, advise subjects regarding permitted emollient(s) and/or sunscreen for use on nontreatment days (use of

emollient(s) on study drug treatment days within 4 hours of study drug application is prohibited), and remind subjects that 24 hours must have elapsed since IP application before the subject's next visit. Subjects should not apply IP on visit days until after the visit. An unscheduled clinic visit may be performed, if necessary.

10.2.4.5 Visit 9 (Week 20; Day 150 ±7 days)

The following procedures will be performed at each study clinic visit:

1. Record concomitant medications and concomitant therapies.
2. Record vital signs (blood pressure and pulse).
3. Record IGA.
4. Record VIIS.
5. Record assessment of roughness.
6. Record palm/sole assessment.
7. Record palm/sole assessment of fissuring.
8. Record ectropion score.
9. Assess and record local tolerance/AEs and review diary.
10. Perform a urine pregnancy test for WOCBP.
11. Collect returned study drug tubes; confirm study drug compliance by weighing returned tube contents and reviewing diaries.
12. Weigh new study drug tubes and dispense enough additional study drug until next visit, and new diary.

10.2.4.6 Visit 10 (Week 24; Day 180 ±7 days) or Early Termination

The following procedures will be performed at Week 24 in the study clinic:

1. Perform a physical examination.
2. Record vital signs (blood pressure and pulse).
3. Record concomitant medications and concomitant therapies.
4. Record IGA.
5. Record VIIS.
6. Assess roughness.
7. Record palm/sole assessment.
8. Record palm/sole assessment of fissuring.
9. Record ectropion score.
10. Assess local tolerance
11. Record AEs and review diary.

12. Perform a 12-lead ECG.
13. Perform a urine pregnancy test for WOCBP.
14. Collect blood and urine for routine laboratory tests (subject must be fasting at least 8 hours).
15. Collect a PK blood sample (all subjects)
16. Collect returned study drug tubes; confirm study drug compliance by weighing returned tube contents and reviewing diaries.

10.2.4.7 Follow-up Evaluation – Open-Label Extension (Week 26/Visit 11)

At 14 days after the last administration of the IP, the following procedures will be performed:

1. Perform a physical examination.
2. Record vital signs (blood pressure and pulse).
3. Record any concomitant medications/therapies.
4. Record IGA.
5. Record VIIS.
6. Assess roughness.
7. Record palm/sole assessment.
8. Record palm/sole assessment of fissuring.
9. Record ectropion score.
10. Assess and record AEs occurring since the last evaluation and review diary.
11. Perform a urine pregnancy test for WOCBP.

10.3. Assessments

The 5-point IGA is a valid measure of disease severity and meets the need for a clinically meaningful measure of success for ichthyosis studies. The IGA scale was developed with the support of experts from academic reference centers for the treatment of ichthyosis. Each level of severity will consider both the severity of scaling and the severity of roughness (Section 10.3.1.2). While retinoid treatment is expected to reduce scale, it may increase erythema; therefore, in this study, erythema will be evaluated as part of local tolerability.

10.3.1 Efficacy Variables

All efficacy measurements will use scales previously used for dermatological studies or as defined in the following sections.

10.3.1.1 Investigator's Global Assessment

The primary endpoint is the number of subjects in each treatment group who experience successful resolution of LI where “success” is defined as clear/almost clear and at least a 2-grade change from Baseline at Week 12/EOT in the Double-blind Period on a 5-point IGA full body scale.

The investigator will rate the subject's condition using the 5-point IGA at each time point shown in the Schedule of Events (Section 2.2).

The IGA will be measured on a 5-point scale, excluding the following areas: knees, elbows, neck, palms, soles, axillae, groin, and scalp:

0	Clear	No scaling and no roughness
1	Almost Clear	Occasional fine scales; hardly palpable roughness (mostly smooth)
2	Mild	Small and fine scales predominate; no more than a few large scales; mild roughness on palpation
3	Moderate	Some large scales that may be thick; coarse roughness on palpation
4	Severe	Confluent, primarily large (>1 cm), thick scales with plate-like hyperkeratosis

